RESEARCH PROTOCOL OUTLINE

Title of Project: CATCH-UP Vaccines: Extension of CATCH-UP (Community - engaged Approaches to Testing in Community and Healthcare Settings for Underserved Populations)

Principal Investigator: [name], PhD, Oklahoma Medical Research Foundation

Co-Principal Investigator: [name], Biostatistics and Epidemiology

Abstract

Our proposal is an extension of the Oklahoma Shared Clinical Translational Resources (OSCTR) project CATCH-UP (Community-engaged Approaches to Testing in Community and Healthcare settings for Underserved Populations) in partnership with the Oklahoma State Department of Health, Southern Plains Tribal Health Board, Latino Community Development Agency, County Health Improvement Organizations, Public Health Institute of Oklahoma, and the Center for Applied Social Research. We will build on existing strengths and infrastructure to improve SARS-CoV-2 vaccine uptake in these highly susceptible populations.

A. Specific Aims

Aim 1 (Preparation). Identify SARS-CoV-2 vaccination barriers/facilitators and assess acceptability and feasibility of a suite of evidence-based vaccine intervention strategies among Oklahoma’s rural, minority, and high-risk populations to inform a targeted multicomponent intervention.

We will conduct up to 10 focus groups including participants from communities with low levels of vaccine uptake and/or high levels of vaccine hesitancy and communities holding events where SARS-CoV-2 testing or vaccination is offered in partnership with the CATCH-UP program (IRB #12582). Focus groups will: (1) explore vaccine-related concerns and motivators, (2) evaluate NIH Community Engagement Alliance (CEAL) educational resources for local and cultural acceptability; and (3) examine outreach and communication intervention strategies detailed in the NIH COVID-19 Vaccination Communication for feasibility at later testing events.

Aim 2 (Optimization). Develop and optimize a multicomponent intervention to improve SARS-CoV-2 vaccination among Oklahoman’s seeking SARS-CoV-2 testing at CATCH-UP testing events.

Aim 2.1. Pilot Implementation. In a pilot implementation, we will randomize participants to either receive a text message (yes/no) and an educational intervention through a tablet compared to a control message. We will also pilot messages for motivational interviewing in tandem with SARS-CoV-2 antibody test results and observe how participants respond to the messages. As part of this study, we will collect

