Overall Study Design: Interventions will address three primary areas to improve vaccination uptake: (1) process (text messages); (2) teachable moment messaging (motivational interviewing); and (3) barrier elicitation and reduction (electronic survey with tailored questions/prompts). In our selection of potential interventions, we will use the Community Preventive Services Task Force (CPSTF)⁹ and the NIH Behavior and Social Sciences Research-Coordinating Committee Rapid Working Group on COVID-19 Vaccine Communication guide, among other resources.¹⁰ We will work with the NIH RADxSM-UP Coordination and Data Collection Center (CDCC) to ensure collection of Common Data Elements.

Table 2. Experimental conditions in the 2³ factorial design for the COVID-19 vaccine intervention

Condition	Factor		
	Process Improvement	Teachable Moment Messaging	Barrier Elicitation and Reduction
1	No	No	No
2	No	No	Yes
3	No	Yes	No
4	No	Yes	Yes
5	Yes	Yes	Yes
6	Yes	Yes	No
7	Yes	No	No
8	Yes	No	Yes

Outcome metrics characterizing SARS-CoV-2 vaccine uptake. Our **primary outcome** will be intention to receive a COVID-19 vaccine post-intervention. We will measure this with the question “How likely are you to get an approved COVID-19 vaccine?” and “If you have received 1 dose of the Janssen vaccine or 2 doses of the Moderna or Pfizer vaccine, how likely are you to get an approved booster shot?” We will compare intention to receive a COVID-19 vaccine or booster among those receiving the interventions compared to those not receiving the intervention (see details on analysis below).

Our **secondary outcome** will be vaccine uptake, including self-report of receiving an initial dose of any approved vaccine, two doses of Pfizer or Moderna vaccines, or a booster of any approved vaccine. We will request the manufacturer of the vaccine and the approximate dates the vaccine was received from the participant.

Aim 2.1. Pilot Implementation.

Study Design. Participants at the pilot sites will be randomized to receive a text message and/or education message (detailed below) delivered through a tablet or no intervention. We will also conduct a pilot of motivational interviewing messages that are tailored based on antibody test results (or lack of testing if the participant declines an antibody test).

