 - c. **Motivational interviewing.** As part of CATCH-UP (IRB #12582), participants currently receive feedback on their antibody test results. Based on focus group findings, we will use a semi-structured script that encourages participants to take actions tailored to their individual test results. The procedure will be as such: Participants are given their test results in line with current CATCH-UP procedures. As part of this protocol, participants will be shown examples of anonymized antibody test results (e.g., results with low and high antibody tests). The key personnel will follow a script in REDCap to interpret the results (or address refusal to receive antibody testing).

These interactions will be observed by key study personnel who will take notes on the participants' reactions to the messages following a checklist directing them to note the antibody results, verbal and non-verbal reactions, as well as fidelity to the semi-structured script. In addition, we will observe the responses of the personnel delivering antibody test results to participants even if they are not using the semi-structured script. The study team will use this information to revise the messaging for full implementation in a future IRB modification. We expect this factor to last approximately 5 minutes.

5. Once the interventions are complete, the participants will complete a brief exit survey that includes questions about their intention to receive a COVID-19 vaccine or booster and to request their contact information for future follow-up surveys and mailing/distribution of gift card (if mailing or emailing is needed). Participants will also be asked to complete a survey required by NIH to report common data elements, with a link sent through text message or email, with follow-up daily for up to three days after the initial survey invitation is sent, and at 30 and 60 days post intervention if the participant has not responded (in tandem with the follow-up survey in #6 below). This will complete the intervention.

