4. Conduct interventions. Participants will be randomized to receive or not receive each of the interventions described below. Participants may be randomized to receive all three factors (treatment), all three control factors, or any combination of treatment/control as defined below (see Table 2). All participants will have the opportunity to receive antibody testing using a finger stick (using the same methods as in the CATCH-UP Study, IRB #12582). After the antibody test is done and participants are waiting for the results (about 15 minutes), the participants will receive the interventions.
 - a. **Text message.** Participants will be randomized to either receive 1) a text message encouraging COVID-19 vaccination (treatment) or no text message (control). This factor will last less than 1 minute.

- a. **Tailored messaging.** Participants will be randomized to receive 1) educational messaging about COVID-19 vaccines (treatment) or 2) attention control educational message not related to COVID-19 (control). This will be delivered on a tablet through RedCap. This factor will last around 10 minutes.
 - b. **Motivational interviewing.** Participants will be randomized to receive feedback on their antibody tests in these two methods: 1) receive a motivational interview following the 5A's strategy (Ask, Advise, Assess, Assist, Arrange) following a semi-structured format (treatment) or 2) interpretation of antibody test results and encouragement of vaccine uptake (as per usual standard practice) (control). Personnel will make notes regarding any deviations from the semi-structure script or assigned treatment arm (e.g., some participants may decline to discuss the vaccine). This factor will last around 5 minutes.
5. Once the interventions are complete, the participants will complete a brief exit survey that includes questions about their intention to receive a COVID-19 vaccine or booster and to request their contact information for future contact and mailing/distribution of gift card (if mailing or emailing is needed). Participants will also be asked to complete a survey required by NIH to report common data elements, with a link sent through text message or email, with follow-up daily for up to three days after the initial survey invitation is sent, and at 30 and 60 days post intervention if the participant has not responded (in tandem with the follow-up survey in #6 below). This will complete the intervention.

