 6. We will send participants a RedCap survey link through text message or email 30 days and 60 days after the intervention to assess intent to be vaccinated for COVID-19 and vaccine uptake, allowing time for both doses of the Pfizer and Moderna, single dose of Jansen's COVID-19 vaccine, or boosters of vaccines to be delivered. We will also send up to three daily reminders to the participant to complete the common data elements survey if they did not complete it after the intervention.
 7. For participants who agree, we will contact up to 60 participants to participate in an evaluation interview to help the personnel determine what did and did not work well during the intervention. This will be a 30 minute to one hour interview.

At all events, key personnel will also conduct a field observation of how the events flow, including external factors such as weather or logistical problems and where challenges to implementing the study or recruiting participants occurred. We will also conduct evaluation focus groups with event site staff to determine what did and did not work during the event.

We expect to recruit 2000 participants over the entire study period (Aim 2.1 and 2.2).

Factorial design. In a factorial research design, two or more independent variables are concurrently examined within the same trial. The three factors are crossed with one another to create a total of eight experimental conditions. An equal number of participants are randomly assigned to each condition, using a random number generator. This is not an 8-arm randomized controlled trial, but instead allows for an efficient examination of main effects for each variable in a sample of 2000 participants (including Aim 2.1 and Aim 2.2).

This approach allows examination of three key treatment development questions in a much more time-efficient and economical manner by simultaneously performing three studies within the single trial. This achieves power to detect between-group differences that is equivalent to performing three separate randomized trials. Investigators who are providing the intervention and conducting analysis will be not be masked to study assignment due to challenges in maintaining the masking in an educational intervention. For all sites, including Aims 2.1 and 2.2, we expect to recruit 2000 participants.

Identifiers might be removed and the de-identified information may be used for future research without additional informed consent from the subject.

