COVID-19 incidence, particularly among underserved minority and rural Oklahomans. Oklahoman's are also reporting SARS-CoV-2 vaccine hesitancy and signs of slowing vaccine uptake, with increased hesitancy among American Indian and rural populations. The project aims to work with ongoing community testing events to implement interventions to improve vaccine uptake among Oklahoma's underserved populations.

I. Statistical Methods

Aim 1 Analysis. Digitally recorded focus groups will be securely uploaded to protected servers and transcribed using NVivo Transcription. Transcriptions will be team coded for conceptual themes using QSR NUDIST Vivo12 Pro for Windows.¹⁶ Investigators will develop a code book. Throughout the coding process, qualitative data will be categorized, connections made between categories, and core categories identified and systematically linked to other categories. Focus group data will inform intervention selection and needed modifications for community acceptability/relevance.

Aim 2 Analysis. All analyses are intent-to-treat. Outcome measures will be assessed at baseline, 30 days, and 60 days follow-up. At the outset, we will examine the frequency distributions of all variables. We will compare the baseline characteristics to assess whether randomization distributed covariates evenly. We will determine whether there is differential dropout and consider developing probability-of-completion weights to obtain unbiased estimates of treatment effect.

The primary analysis will assess the effects of each intervention component in terms of its association with the primary outcome (intent to receive a COVID-19 vaccine immediately after the interventions are completed). Cross-sectional analyses will be conducted for outcomes assessed at 30 and 60 days. For binary outcomes, chi-square tests will be used to compare the outcomes between groups. For continuous outcomes, two-sample t-tests or Wilcoxon rank sum tests, whichever is more appropriate, will be used to compare between groups. A longitudinal analysis using Generalized Estimating Equations (GEE) techniques will also assess the overall impact of the intervention by including data from all follow-up time points.

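### The plan gives 2000 participants for every main effect, but motivational interviewing is first randomised in Aim 2.2, so its randomised sample is about 1500 and no rule excludes the pilot

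*Combined protocol and SAP*

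**What the plan says.** **Sample for each factor.** Section D, Factorial design, says the trial "allows for an efficient examination of main effects for each variable in a sample of 2000 participants (including Aim 2.1 and Aim 2.2". The total of 2000 expected recruits is also given separately in the same part of the protocol, so this sentence is about the analysis sample and not only about recruitment.

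**What the pilot randomises.** Section A, Aim 2.1: "we will randomize participants to either receive a text message (yes/no) and an educational intervention through a tablet compared to a control message". Section D, Aim 2.1, Study Design: "Participants at the pilot sites will be randomized to receive a text message and/or education message". Both name two factors.

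**MI in the pilot.** The same Study Design paragraph adds: "We will also conduct a pilot of motivational interviewing messages that are tailored based on antibody test results". Item 4c of the Aim 2.1 Intervention Procedure describes a script, observers and a checklist. It also provides for observing staff who are not using the script. It gives no allocation and no control arm, whereas items 4a and 4b each state that participants are randomised. Item 4c continues: "The study team will use this information to revise the messaging for full implementation in a future IRB modification".

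**MI in Aim 2.2.** Item 4 of the Aim 2.2 Intervention Procedure then defines two MI arms: "Participants will be randomized to receive feedback on their antibody tests in these two methods".

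**Analysis.** Section I, Aim 2 Analysis: "The primary analysis will assess the effects of each intervention component in terms of its association with the primary outcome", and "All analyses are intent-to-treat". The sample size paragraph puts the pilot at an estimated 500 participants and bases power on both phases, with no exception for MI.

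**The concern.** For MI these statements cannot all hold. About a quarter of the 2000 have no assigned MI arm, so they cannot contribute to an intention-to-treat comparison of MI with its control. Either they are excluded and the stated 2000 is wrong for this factor, or they are included and the contrast is not fully randomised. No section says which.

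Two things are at stake. The first is precision: the sample claimed for one of three primary contrasts is larger than the design can supply. The second is validity if the gap were filled badly. Pilot participants were not randomised to MI, heard the script in use before its revision, and came from the earlier phase. Classifying them by whether they heard the script would mix those differences into the MI effect. The plan does not specify that analysis, but nothing in it rules it out. The same document says that those conducting the analysis will not be masked, which is a further reason to fix the analysis set in advance.

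**Working it through.** **Inputs from the protocol.** Total 2000, expected, both phases (Factorial design). Pilot 500, estimated (Sample size and power calculations). Equal allocation to eight conditions, hence 1:1 on each factor (Factorial design). Type I error 0.05, SD 5, mean difference 20, power over 80% (Sample size and power calculations).

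**Assumptions.** Two-sided test, individual-level two-sample comparison, pilot range of 300 to 700, and 35% of controls likely to accept vaccination for the percentage-point version.

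**1. The plan's own figures.** The 2000 is not derived from a formula, and the number of sites does not appear in the power sentence, so neither can be reproduced exactly. The power claim holds as a lower bound: 20/5 = 4 SD gives power of about 100% even with a single site of 167 participants, with or without a design effect of 1 + (167 - 1) × 0.01 = 2.66.

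**2. Head count for MI.** 2000 - 500 = 1500, or 750 v 750. For a pilot of 300 or 700 it is 1700 or 1300.

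**3. Precision.** The SE ratio is sqrt(2000/N). The detectable difference at 80% power is 2.802 × sqrt(2/(N/2)) SD, where 2.802 = 1.960 + 0.842.

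| N for MI | SE relative to 2000 | Detectable difference (SD) | Detectable difference (points, 35% in controls) |
|---|---|---|---|
| 2000 | 1.000 | 0.125 | 6.1 |
| 1700 | 1.085 | 0.136 | 6.6 |
| 1500 | 1.155 | 0.145 | 7.0 |
| 1300 | 1.240 | 0.155 | 7.55 |

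An effect with 80% power at 2000 has about 68% at 1500. A common design effect would change the SD figures but not the ratios.

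**4. If pilot participants were pooled by exposure, without stratification.** Let s pilot participants count as having had MI and u as controls, with 750 per arm from Aim 2.2. The share of any pilot-versus-later difference in intention that enters the MI estimate is s/(750 + s) - u/(750 + u). The last two columns assume no MI effect, a 35% base rate and a 10-point difference between phases.

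| s / u | Share | Bias (points) | Two-sided rejection rate |
|---|---|---|---|
| 500 / 0 | 500/1250 = 0.40 | 4.0 | about 44% |
| 400 / 100 | 400/1150 - 100/850 = 0.23 | 2.3 | about 18% |
| 250 / 250 | 0 | 0 | 5% |

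The worst-case share is 300/1150 = 0.26 for a pilot of 300 and 700/1350 = 0.52 for a pilot of 700. On a continuous scale, with all 500 counted as treated, phase differences of 0.1, 0.2 and 0.3 SD give biases of 0.04, 0.08 and 0.12 SD and rejection rates of about 14%, 41% and 74%.

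**The case against.** The best defence is that intention-to-treat compares people by assigned arm. Pilot participants have no MI assignment, so they drop out of that contrast without further instruction. The sample size paragraph does describe the comparison by receipt of a component, but it is a power paragraph and does not define an analysis set. On this view the validity problem is hypothetical. The bias figures need a departure from intention-to-treat, unstratified pooling, a chosen split and a chosen phase difference, none of which comes from the protocol. The precision loss is modest, leaves the stated power claim intact, and matters less in what the Aim 2.2 Study Design calls an initial pilot/feasibility study.

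Much of this stands. Excluding the pilot is the natural reading, and the pooled scenario only illustrates what the missing rule permits, down to no harm at all with an even split. But the defence does not rescue the sentence at issue: if intention-to-treat excludes the pilot, 2000 is wrong for MI. The intact power claim is also little comfort, since a 4 SD difference says nothing useful about precision.

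Two further caveats are fair. The 1500 is approximate, because 500 is an estimate, 2000 is an expectation, and the text speaks of several pilot sites in one place and a single site in another. And 2000 for text and education assumes 1:1 allocation in the pilot, which is not stated. Their content may also change after it, since Section A, Aim 2.2, lets pilot feedback shape the components.

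**Conclusion.** The concern holds. The sample stated for each main effect is not available for MI. Its randomised sample is about 1500 instead of 2000, a quarter smaller, with a 15.5% larger standard error (8.5% to 24% for an assumed pilot of 300 to 700). No rule keeps pilot participants out of the MI contrast. The head count rests only on the protocol's own estimates. The percentage-point figures rest on the assumed 35%, and the bias figures on pooling that the plan does not specify. The randomised MI comparison within Aim 2.2 is itself sound. The text should be corrected before analysis because it misstates the size, and leaves open the membership, of a primary contrast.

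**What to change.** 1. In Section I, Aim 2 Analysis, state that the MI main effect, and any interaction involving MI, uses only participants randomised in Aim 2.2.
2. In the Factorial design paragraph, replace the single 2000 with a sample for each factor: about 1500 for MI, and up to about 2000 for text and education if the phases are combined.
3. In the sample size paragraph, give a detectable difference for each factor.
4. Say that equal allocation to eight conditions applies to Aim 2.2, where that sentence is correct.

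Including phase and site as strata or fixed effects when text and education are combined across phases would be good practice, but this repair does not depend on it.

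The cost is wording only, with no new data or procedures. The one downside is a slightly less favourable stated sample and precision for MI.
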